6.5.1.3 Guidelines for the treatment of alpelisib-induced hyperglycemia

Alpelisib, like other PI3K inhibitors, may affect glucose homeostasis which could result in increases of plasma glucose and insulin resistance ([Busaidy et al 2012](#)). Alpelisib induced hyperglycemia is generally manageable with adequate anti-diabetic treatment. Alpelisib induced hyperglycemia typically occurs within the first month of treatment. Participants with pre-diabetes (i.e. FG 100 to 125 mg/dl; 5.6 to 6.9 mmol/L) and those with an established diagnosis of type 2 diabetes mellitus should be monitored carefully, thus allowing an early detection and prompt management of increases in fasting glucose while on alpelisib treatment. However all participants, even those with fasting glucose within normal limits at screening, may develop alpelisib-induced hyperglycemia which is an on-target effect seen with PI3K inhibitors. Participants should always be instructed to follow dietary guidelines provided by the ADA and/or the European Association for the study of Diabetes, e.g. small frequent meals, low carbohydrate content, high fiber, balancing carbohydrates over the course of the day; three small meals and 2 small snacks rather than one large meal and exercise, as appropriate.

Detailed guidelines for management of alpelisib induced hyperglycemia is provided in [Table 6-3](#) "Criteria for dose reduction/interruption and re-initiation of alpelisib treatment for adverse drug reactions" and detailed guidelines on use of oral anti-diabetics is provided in [Section 6.2.1.1](#) "Permitted concomitant medications". In brief, this includes early administration of metformin or a SGLT2 inhibitor (alone or in combination with metformin). Metformin may be titrated to a daily dose of 1000 mg twice a day. Since SGLT2 inhibitors may increase the risk of euglycemic diabetic ketoacidosis, serum ketones levels will be assessed throughout the trial in participants treated with SGLT2 inhibitors at screening, Day 1 of each cycle, and at end of trial.

Local standard clinical practice may be followed for monitoring and managing hyperglycemia. Fasting glucose testing will be performed both locally (at home using a glucometer or at a local laboratory) and/or at the investigative site for rapid availability for safety evaluation and

management guidance. Laboratory confirmation of self-measured high glucose values may be requested if deemed necessary by the investigator. The investigator will use clinical judgment to guide the management plan of each participant based on individual benefit/risk assessment.

Special attention should be paid to the risk of hypoglycemia in participants interrupting alpelisib treatment and concomitantly receiving insulin and/or sulfonylureas. Due to the short half-life of alpelisib, all glucose lowering medications should be discontinued when alpelisib is stopped.

If metformin or an anti-diabetic agent is interrupted for radiologic assessments or another reason, then alternative hyperglycemia management should be considered for those days to ensure optimal hyperglycemia management.

Consultation with a diabetologist or HCP experienced in the management of hyperglycemia is highly recommended for better assessment and management of alpelisib-induced hyperglycemia.

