Grade 3 (FG > 250 to 500 mg/dL) [> 13.9 to 27.8 mmol/L]	
 Omit alpelisib and confirm fasting status of the assessment. If non-fasting, re-check within 24 hours. 
Regardless of fasting status, consider IV fluids if symptoms of hyperglycemia or signs of volume depletion.
 
Exclude confounding factors like e.g. urinary tract and consider consultation with a diabetologist.
 
Administer intravenous hydration and intervention for electrolyte/ketoacidosis/hyperosmolar disturbances as clinically appropriate. Insulin may be used for 1 to 2 days until hyperglycemia resolves, however this may not be necessary in the majority of alpelisib-induced hyperglycemia given the short half-life of alpelisib.
 
Start or further intensify oral anti-diabetic treatment and titrate as outlined for Grade 2.
 
Monitor fasting glucose levels as clinically indicated and at least twice weekly until FG resolves to ≤ Grade 1.
 
 If FG resolves to ≤ 160 mg/dL within 3 to 5 days, while off alpelisib and on metformin, re-start alpelisib and reduce 1 dose level, continue with anti-diabetic treatment. A second and third oral hypoglycemic agent may be initiated concomitantly, if needed, in consultation with a diabetologist. Check FG at least weekly for 8 weeks, then continue checking at least every 2 weeks, alert treating physician if FPG > 250 mg/dL. If FG does not resolve to ≤ 160 mg/dL within 3 to 5 days while off alpelisib and on metformin, consultation a diabetologist for management of diabetes is strongly recommended. If FG does not resolve to ≤ 160 mg/dL within 21 days after institution of appropriate anti-diabetic treatment in cooperation with diabetologist and exclusion of confounding factors e.g. urinary tract infection, permanently discontinue participant from alpelisib treatment.

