Grade 4 (FG > 500 mg/dL) [≥ 27.8 mmol/L]	
 Omit alpelisib confirm fasting status of the assessment. If non-fasting, re-check within 24 hours. 
Regardless of fasting status, consider IV fluids.
 
 Exclude confounding factors like e.g. urinary tract infection. Consult with diabetologist, initiate or intensify medication with appropriate anti-diabetic treatment (see Grade 3), re-check within 24 hours. If grade improves then follow specific grade recommendations If FG is confirmed as > 500 mg/dL and confounding factors could be excluded, permanently discontinue participant from alpelisib.
CTCAE v 4.03 is modified to allow fasting blood glucose values in addition to fasting plasma glucose values. * For specific recommendations please see Section 6.5.1.3 "Guidelines for the treatment of alpelisib induced hyperglycemia"	
Investigations (Hepatic) . Note: this is for newly occurred or worsened from baseline	
Isolated total Bilirubin elevation	

Dose Modifications for alpelisib as specified below. Combination drug may be continued while alpelisib dose is being held, at the investigators discretion, and as specified.	
Worst toxicity - CTCAE Grade (value)	Dose Modifications for alpelisib
Grade 1 (> ULN - 1.5 × ULN)	
 No dose adjustment is required. Initiate appropriate medical therapy and monitor as clinically indicated.
Grade 2 (> 1.5 to 3.0 × ULN)	
 Interrupt dose until recovery to Grade ≤ 1 and resume at the same dose if resolved in ≤ 14 days or resume at the next lower dose level if resolved in > 14 days.
Grade 3 (> 3.0 to 10.0 × ULN)	
 Interrupt dose until recovery to Grade ≤ 1, then resume at the next lower dose level.
Grade 4 (> 10.0 × ULN)	
 Permanently discontinue.
Isolated AST or ALT elevation	
Grade 1 (> ULN - 3.0 × ULN)	
 No dose adjustment is required. Initiate appropriate medical therapy and monitor as clinically indicated.
Grade 2 (> 3.0 to 5.0 × ULN)	
 Interrupt dose until recovery to Grade ≤ 1, then decrease dose level.
Grade 3 (> 5.0 to 20.0 × ULN)	
 Permanently discontinue.

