6.5.1 Follow-up for toxicities

Participants, whose treatment is interrupted or permanently discontinued due to an AE or a clinically significant laboratory value, must be followed until resolution or stabilization of the event (and/or up to EOT visit), whichever comes first. Further guidelines and recommendations for the management of specific trial treatment combination-induced toxicities are provided below.

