8.4.3 Laboratory evaluations

Clinical laboratory analyses are to be performed on-site at Screening (Day -28 to Day -1), Cycle 1, Day 1, and at the EOT visit, and at a local laboratory during remote participation. SMBG will be performed by the participant. Novartis must be provided with a copy of all the laboratories' certification (if applicable), and a tabulation of the normal ranges and units of each parameter collected in the CRF. Any changes regarding normal ranges and units for laboratory values assessed during the trial must be reported via an updated tabulation indicating the date of revalidation.

The laboratory evaluation collection plan is presented in [Table 8-4](#). Visit windows of \pm 3 days are allowed for laboratory evaluations.

The investigator is responsible for reviewing all laboratory reports for participants in the trial and evaluating any abnormalities for clinical significance. Clinically significant abnormalities must be recorded as either medical history/current medical conditions or AEs as appropriate. At any time during the trial, abnormal laboratory parameters which are clinically relevant and require an action to be taken with trial treatment (e.g., require dose modification and/or interruption of trial treatment, lead to clinical symptoms or signs, or require therapeutic intervention), whether specifically requested in the protocol or not, will be recorded on the AE eCRF page. Laboratory data will be summarized using the CTCAE version 4.0.3.

Unscheduled assessments may be performed if medically indicated to assess a (potential) AE or when needed by the treating physician for decision making (e.g. dose modifications).

Table 8-4 Laboratory evaluation collection plan

Test Category	Test Name	Screening Day -14 to Day -1	Treatment phase	End of Trial Visit
Hematology	Hemoglobin, White blood cells, Differential (Leukocytes, Neutrophils, Thrombocytes), and Platelets.	Mandated	D1 of Cycle 2, and thereafter Day 1 of each cycle	Mandated
Chemistry	For all participants: C-Reactive Protein, Albumin, Alkaline Phosphatase, alanine aminotransferase, Aspartate aminotransferase, Bilirubin, Creatinine, Sodium, Potassium, Cancer Antigen 15-3, Lactate Dehydrogenase (LDH). For participants treated with SGLT2 inhibitors with or without metformin: ketones	Mandated	D1 of Cycle 2, and thereafter Day 1 of each cycle	Mandated

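### Section 6.5.1.3 withdraws all glucose-lowering drugs when alpelisib is stopped, with no glucose condition, although Table 6-3 stops alpelisib permanently in participants whose glucose is still uncontrolled

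*Protocol*

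**What the plan says.** Protocol Section 6.5.1.3 first warns of hypoglycemia in participants who interrupt alpelisib while on insulin or a sulfonylurea. It then gives the short half-life of alpelisib as the reason why "all glucose lowering medications should be discontinued when alpelisib is stopped". It attaches no glucose threshold, taper or exception.

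Table 6-3 (Section 6.5) stops alpelisib permanently for hyperglycemia in two situations:

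- **Grade 3.** Alpelisib is omitted and oral anti-diabetic treatment is started or stepped up. If fasting glucose is not at or below 160 mg/dL in 3 to 5 days, "consultation a diabetologist for management of diabetes is strongly recommended". If it has still not reached that level "within 21 days after institution of appropriate anti-diabetic treatment in cooperation with diabetologist", and confounders have been excluded, alpelisib is stopped for good.
- **Grade 4.** The site is to consult a diabetologist, "initiate or intensify medication with appropriate anti-diabetic treatment", and re-check within 24 hours. The row ends with the case in which a value above 500 mg/dL is confirmed and "confounding factors could be excluded, permanently discontinue participant from alpelisib".

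Section 6.5.1 says that participants who stop treatment for an adverse event "must be followed until resolution or stabilization of the event (and/or up to EOT visit), whichever comes first". It does not say whether glucose-lowering treatment continues in the meantime.

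**The concern.** The sentence suits the participant whose glucose falls as alpelisib clears; there, continued insulin or a sulfonylurea risks hypoglycemia. It does not suit the participant who is taken off alpelisib because glucose would not come down, and its wording does not separate the two. A site applying it as written would withdraw anti-diabetic drugs from someone still hyperglycemic, shortly before trial follow-up may end. What is at stake is the safety of a few participants. The primary endpoint, participant satisfaction, is not involved.

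**Working it through.** This is mainly a comparison of text. Arithmetic serves only to bound the scale.

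**1. Grade 3 stop.**
- Alpelisib has been omitted since the Grade 3 value was found. The row's only stated route back to the drug requires fasting glucose at or below 160 mg/dL.
- A participant who reaches the 21-day rule is therefore off alpelisib, on anti-diabetic treatment, and still above 160 mg/dL.
- Section 6.5.1.3 would now withdraw that treatment because alpelisib clears quickly. The drug has already been withheld, so the reason no longer applies. The same row treats the condition as diabetes needing specialist management.

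**2. Grade 4 stop.**
- Treatment has just been started or increased, and a re-check within 24 hours has confirmed a value above 500 mg/dL.
- The permanent stop then triggers the Section 6.5.1.3 sentence, which would remove the drugs the row has just called for. Glucose may well fall as alpelisib clears, but the sentence does not wait for that.

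**3. Is there a condition elsewhere?** Table 6-3 and Sections 6.2.1.1, 6.5.1 and 9 contain no statement that glucose-lowering treatment is kept until glucose recovers after a permanent stop. The neighbouring Section 6.5.1.4 shows that such a condition can be written: after discontinuation for pancreatic toxicity, it requires weekly monitoring until Grade 1 or lower, or stabilization.

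**4. Scale.**
- Inputs: 18 of 284 SOLAR-1 participants stopped alpelisib for hyperglycemia (Section 6.2.1.1); about 20 participants planned (Section 12.8).
- Rate: 18 / 284 = 6.34%, which matches the 6% in Section 6.2.1.1 and the 6.3% in Section 1.1.
- Expected stops for hyperglycemia among 20: 20 × 0.0634 = 1.27.
- Exact (Clopper-Pearson) 95% interval for the rate: 3.80% to 9.83%, or 0.76 to 1.97 of 20.

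The 1.27 counts every stop for hyperglycemia. Only stops made while glucose was still uncontrolled are relevant, and the documents do not say how many of the 18 were of that kind. The figure is therefore a ceiling on the expected number, and the interval describes all such stops, not the affected subgroup.

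**The case against.** The strongest reply is that other text governs. Section 4.5.1 obliges the investigator to use medical judgment in deciding care for any adverse event, whereas the criticised sentence only says *should*. Section 6.2.1.1 directs that hyperglycemia arising in the trial be treated according to ADA guidance, and does not limit this to time on alpelisib. Section 10.1.1 requires adverse events to be treated appropriately, although the list beneath it concerns actions with the trial drug. Section 6.5.1.3 itself allows local practice and clinical judgment. The Grade 4 row instructs consultation with a diabetologist, and the Grade 3 clock runs on treatment given together with one. The preceding sentence also shows that the aim is to avoid hypoglycemia, which is legitimate.

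All of this stands, and it makes literal compliance unlikely. None of it puts a condition on the sentence, which still gives the wrong instruction for the two stops that Table 6-3 requires.

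Three stronger readings are tempting, and the documents do not support them:

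- **That the sentence also covers temporary holds and so contradicts Table 6-3.** The paragraph contrasts interrupting with stopping. The glossary and Section 9.1.1 use stopping for discontinuation, and Table 6-3 speaks of omitting or interrupting. For a Grade 3 hold that resolves, the table already governs: "while off alpelisib and on metformin, re-start alpelisib and reduce 1 dose level, continue with anti-diabetic treatment".
- **That it withdraws diabetes drugs taken before the trial.** Controlled type 2 diabetes is eligible and the word *all* is literal. But the half-life reason and the section title both point to drugs given for alpelisib-induced hyperglycemia.
- **That Section 9.2 leaves participants without diabetes care.** That passage concerns access to the trial drugs and presupposes usual care. Section 6.7.1.2 already places SGLT2 inhibitors and metformin under standard reimbursement.

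**Conclusion.** The concern holds as a minor participant-safety wording correction. Followed literally, Section 6.5.1.3 removes anti-diabetic treatment in both situations where Table 6-3 stops alpelisib for uncontrolled glucose. The Grade 3 case is the clearer one, because the half-life reason has already run out.

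The number affected is small and unknown, with an expected count of at most about 1 of 20 planned participants. That rests on the SOLAR-1 rate carrying over. Prophylactic SGLT2 inhibitors and the entry limits on fasting glucose and HbA1c could lower it. SAP Section 1 reports early termination for low enrollment without giving the number enrolled, so the real count would be lower still. If nobody remains on treatment, the correction matters only where this guidance is reused.

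A reader might infer that harm is likely, or that the affected share of stops can be estimated. The safeguards above argue against the first, and the documents give no figure for the second.

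**What to change.** Replace the sentence in Section 6.5.1.3 with:

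*After permanent discontinuation of alpelisib, reduce and stop anti-diabetic drugs started for alpelisib-induced hyperglycemia as fasting glucose recovers (Grade 1 or lower, or baseline), with glucose monitoring and particular attention to hypoglycemia with insulin or sulfonylureas. If glucose has not recovered by the EOT visit, hand over glucose management to usual care or a diabetologist.*

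Temporary holds need no added text, since Table 6-3 covers them. Grade 1 or lower corresponds to the 160 mg/dL that Table 6-3 uses for restarting alpelisib. Using it to guide withdrawal is a choice, and the words about recovery and baseline leave room for clinical judgment.

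The cost is two sentences and a handover step for the few participants who leave with raised glucose. No new visit is needed: "Clinical laboratory analyses are to be performed on-site at Screening (Day -28 to Day -1), Cycle 1, Day 1, and at the EOT visit". A letter to sites is worthwhile only if participants are still on treatment.

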6.5.1.4 Follow-up on amylase or lipase elevation (\geq CTCAE Grade 3)

Participants with amylase or lipase elevation \geq CTCAE Grade 3 must be tested weekly (or more frequently if clinically indicated) until \leq Grade 1 (or baseline). After resumption of dosing, continue to test weekly for one additional cycle. If no reoccurrence of \geq Grade 2 event, continue monitoring every cycle.

An exception to these follow-up guidelines will be made for cases of isolated amylase elevations in which amylase fractionation demonstrates that pancreatic amylase is \leq Grade 1. In such cases, total amylase and fractionated amylase should be monitored weekly (or more frequently if clinically indicated) for 4 weeks. If pancreatic amylase remains \leq Grade 1, subsequent monitoring must be performed at least every 4 weeks (or more frequently if clinically indicated).

Participants who discontinue trial treatment due to pancreatic toxicity must be monitored weekly (or more frequently if clinically indicated) until the event resolves to \leq Grade 1 or stabilization occurs (no CTCAE v4.03 grade change over 4 weeks).

If amylase and/or lipase elevations are accompanied by new or progressive unexplained abdominal symptoms such as severe pain or vomiting, withhold trial treatment, then perform diagnostic procedures (e.g., abdominal CT scan or ultrasound) to exclude pancreatic pathology.

See also dose modification guidelines described in [Table 6-3](#) “Criteria for dose reduction/interruption and re-initiation of alpelisib for adverse drug reactions”.

Perform relevant examinations (ultrasound or MRI, Endoscopic Retrograde Cholangiopancreatography) as appropriate, to rule out an extrahepatic cause of cholestasis. Cholestasis is defined as an ALP elevation $> 2.0 \times \text{ULN}$ with R value < 2 in participants without bone metastasis, or elevation of the-specific ALP isoenzyme in participants with bone metastasis.

Note: The R value is calculated by dividing the ALT by the ALP, using multiples of the ULN for both values. It denotes the relative pattern of ALT and/or ALP elevation is due to cholestatic ($R \leq 2$), hepatocellular ($R \geq 5$), or mixed ($R > 2$ and < 5) liver injury. In clinical situations where it is suspected that ALP elevations are from an extrahepatic source, the GGT can be used if available. GGT may be less specific than ALP as a marker of cholestatic injury, since GGT can also be elevated by enzyme induction or by ethanol consumption. It is more sensitive than ALP for detecting bile duct injury (livertox.nih.gov/rucam.html).

If DILI confirmed: permanently discontinue trial treatment.

If DILI is unlikely: interrupt treatment. Treat identified cause according to institutional guidelines. If resolved, reduce by one dose level. Re-administration of trial treatment should be considered only if the investigator assesses benefit to outweigh the risk. Any decision regarding re-administration of trial drug/s and dose regimen should be discussed with the Novartis medical safety team.

Table 6-5 “Alternative causes of liver disease” provides guidance on specific clinical and diagnostic assessments which can be performed to rule out possible alternative causes of observed liver function test abnormalities.

Table 6-5 Alternative causes of liver disease

Disease	Assessment
Hepatitis A, B, C, E	IgM anti-HAV; HBsAg, IgM anti-HBc, HBV DNA; anti-HCV, HCV RNA, IgM & IgG anti-HEV, HEV RNA
Cytomegalovirus (CMV), Herpes Simplex Virus (HSV), Epstein-Barr virus (EBV) infection	IgM & IgG anti-CMV, IgM & IgG anti-HSV; IgM & IgG anti-EBV
Autoimmune hepatitis	ANA & ASMA titers, total IgM, IgG, IgE, IgA
Alcoholic hepatitis	Ethanol history, gammaGT, MCV, CD-transferrin
Nonalcoholic steatohepatitis	Ultrasound or MRI
Hypoxic/ischemic hepatopathy	Medical history: acute or chronic CHF, hypotension, hypoxia, hepatic venous occlusion. Ultrasound or MRI.
Biliary tract disease	Ultrasound or MRI, ERCP as appropriate.
Wilson disease	Caeruloplasmin
Hemochromatosis	Ferritin, transferrin
Alpha-1-antitrypsin deficiency	Alpha-1-antitrypsin

Following appropriate causality assessments, as outlined above, the causality of the drug is estimated as “probable” i.e. > 50% likely, if it appears greater than all other causes combined. The term “drug-induced” indicates probably caused by the drug, not by something else, and only such a case can be considered a DILI case and should be reported as an SAE.

Following appropriate causality assessments, as outlined above, the causality of the drug is estimated as “probable” i.e. > 50% likely, if it appears greater than all other causes combined. The term “drug-induced” indicates probably caused by the drug, not by something else, and only such a case can be considered a DILI case and should be reported as a serious AE (SAE).

6.5.1.6 Guidelines for hypersensitivity

Alpelisib and combination drug are associated with hypersensitivity reactions, including anaphylaxis. These are manifested by symptoms including, but not limited to, dyspnea, flushing, rash, fever or tachycardia. Alpelisib and/or combination drug should be permanently discontinued and should not be re-introduced in participants with serious hypersensitivity reactions. Appropriate treatment should be promptly initiated.

6.6 Additional treatment guidance

6.6.1 Trial treatment compliance

Participants or caregivers will complete a medication diary during the entire trial through the telemedicine application to report compliance.

